3.3 Design and Procedure

Subjects with advanced EOC (including primaries of ovarian, Mullerian, fallopian tube, or peritoneal origin) will be screened for eligibility at Duke Gynecology Oncology clinic visits prior to initiation of NACT. Selection criteria are detailed in a subsequent section. Once determined eligible, a provider will approach the patient and inquire about interest in participating in the study. If the patient desires to receive more information, clinical research personnel will discuss the study with patient and obtain informed consent if all selection criteria are met (detailed in a subsequent section). If the research team is unable to meet with a patient face to face but the patient is interested in participating, the same process will be facilitated via telephone once secure identifiers are met. If the patient consents, they will then be considered an enrolled study subject. Electronic consent will be performed in REDcap. Following enrollment, basic demographic information for each patient will be recorded in a secure REDCap database. Specific demographic data and security concerns are further outlined in a later section.

Patients will be enrolled and will receive aspirin at the Macon Pond location. All study activities will be performed by the study coordinators, so we do not anticipate needing assistance from the Duke Raleigh study team.

The primary selection criterion is a Khorana score of 1; additional criteria are detailed in a subsequent section. The Khorana score will be calculated according to the following parameters in closest proximity to the first cycle of chemotherapy: 1 point for gynecologic cancer, 1 point for BMI ≥ 35 , 1 point for Hgb < 10 or use of red blood cell growth factors, 1 point for leukocyte count $> 11,000$, and 1 point for platelets $\geq 350,000$. Patients therefore have a baseline Khorana score of 1 and are ineligible if any additional Khorana score parameters are met. Prior to the April 2021 amendment, Khorana score was not a part of the inclusion criteria. Any existing patient with a Khorana score of more than 1 who is receiving study drug at the time the amendment is approved will be contacted by the study PI to discuss switching to a DOAC. The patient will have the option to remain on study and complete their aspirin regimen or come off study and begin a

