DOAC instead. Any existing patients with a Khorana score of more than 1 who have already completed their aspirin regimen and are considered "on follow up" will remain on study.

Once enrolled in the study, subjects will receive a 30-day supply of low dose aspirin from a study team member and will be instructed to start taking one 81 mg tablet daily starting the first day of their first neoadjuvant chemotherapy cycle. Subjects may also be consented after the first day of their first cycle so long as they are taking the aspirin by the end of the day of their second cycle. Patients who are already on low dose aspirin for another indication will still be eligible for the study but will be instructed to take the study drug such that adherence can be monitored. These patients will continue their prior regimen following completion of NACT. Participants will be instructed to complete medication adherence diaries and AE symptom questionnaires. At each subsequent clinic visit for consideration of an additional NACT cycle, a member of the research team will review medication adherence diaries and AE symptom questionnaires and administer the Voils DOSE-Nonadherence measure survey. If symptoms are concerning for a potential AE, the research team personnel will inquire further and discuss with the PI. Please see subsequent sections related to AE monitoring and reporting. No additional components of history and physical exam will be completed outside standard of care performed by the patient's provider prior to initiation of an additional cycle of NACT. Different patients may undergo different numbers of NACT cycles, and thus the 30-day supply of aspirin will be refilled by a member of the research team when the decision is made to proceed with an additional cycle.

Participants who experience clinically significant adverse drug events such as bleeding or medication intolerance will be withdrawn from the study. Subjects with significant chemotherapy-induced thrombocytopenia (platelet count less than 50,000) will be instructed to stop taking daily aspirin for 1 week until platelet counts normalize. If a subject withdraws from the study voluntarily, there will be no further follow up. If a participant is censored due to development of a VTE or clinically significant AE, the research team will continue to collect clinical data until the end of the predetermined follow up period.

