7.4 Definition of Evaluable Subjects, On Study, and End of Study

Evaluable subjects are participants who are enrolled in the study, given the study drug (aspirin) and receiving NACT until interval debulking surgery.

On study participants are those who are receiving aspirin or who are censored due to VTE or AE but for whom clinical data is still being collected.

End of study is defined as one year from the investigation start date.

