11.1 Adverse Events

An adverse event (AE) is any untoward medical occurrence in a subject receiving study therapy and which does not necessarily have a causal relationship with this treatment. For this protocol, the definition of AE also includes worsening of any pre-existing medical condition. An AE can therefore be any unfavorable and unintended or worsening sign (including an abnormal laboratory finding), symptom, or disease temporally associated with the use of study therapy, whether or not related to use of the study therapy. Abnormal laboratory findings without clinical significance (based on the PI's judgment) should not be recorded as AEs. But laboratory value changes that require therapy or adjustment in prior therapy are considered adverse events.

From the time the subject signs the informed consent form through the End of Study visit (as defined in Section 10.3), all AEs must be recorded in the subject medical record and adverse events case report form.

AEs will be assessed according to the CTCAE version 4.0. If CTCAE grading does not exist for an AE, the severity of the AE will be graded as mild (1), moderate (2), severe (3), life-threatening (4), or fatal (5).

Attribution of AEs will be indicated as follows:

- Definite: The AE is clearly related to the study therapy
- Probably: The AE is likely related to the study therapy
- Possible: The AE may be related to the study therapy
- Unlikely: The AE is doubtfully related to the study therapy
- Unrelated: The AE is clearly NOT related to the study therapy

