13.1 Analysis Sets

The analysis set will include data from the study cohort for the duration of the defined study period. Considerations for data analysis are outlined below.

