8.7.2. Statistical Hypothesis, Model, and Method of Analysis

The goal for initiating accrual into this study will be September 1st, 2020. Patients will continue to be enrolled through December 30th, 2021. Subjects will be followed through the primary NACT treatment course until interval debulking surgery, with an estimated duration of 6-9 months following enrollment depending on the number of NACT cycles the individual undergoes. The primary efficacy outcome of this study is rate of VTE among the study cohort during NACT. The primary safety outcome is the incidence of clinically significant adverse drug events. Data from medication adherence diaries and AE symptom questionnaires will be reviewed and entered into the REDCap database. An intention-to-treat analysis will be performed. Subjects withdrawn due to medication intolerance or adverse drug events will be censored, and the research team will continue to collect clinical data for the predetermined follow up period.

We will calculate the incidence of VTE during the study period defined above (enrollment to interval debulking surgery or 1 week after completion of the primary neoadjuvant chemotherapy course if debulking surgery is deferred) and estimate a 95% exact binomial confidence interval. Since this is a pilot study, the incidence of venous thromboembolism in the study population will be compared to a historical control from a previous research study

of the incidence of venous thromboembolism among women receiving neoadjuvant chemotherapy for advanced ovarian cancer in which the majority of patients were from Duke. A drop greater than 20% (from approximately 8% to 6.4%) in the rate of venous thromboembolism would be considered clinically meaningful. If the true VTE rate is 6.4%, the width of the 95% exact binomial confidence interval will be 0.098. We will also monitor for adverse safety events related to low dose aspirin use, including major or minor bleeding events, gastrointestinal complications, and medication intolerance (side effects or adverse reaction). Further detail regarding AE monitoring and reporting is outlined in a previous section.

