8.7.3. Handling of missing values, censoring, and discontinuations

An intention-to-treat analysis will be performed for all enrolled subjects. Due to the small sample size, we will not impute missing data. If a participant is censored due to the occurrence of a VTE or a significant AE, the study team will continue to collect clinical data until the predetermined follow up period is complete.

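### Section 13 assigns only all enrolled (consented) women to an analysis, so on its natural reading women who never took study aspirin enter the denominator of the primary safety rate

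*Combined protocol and SAP*

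**What the plan says.** **Who is enrolled, and when drug is given.** Section 3.3 (Design and Procedure) ties enrolment to consent: "If the patient consents, they will then be considered an enrolled study subject". Supply comes next: "Once enrolled in the study, subjects will receive a 30-day supply of low dose aspirin from a study team member". The first tablet is planned for day 1 of the first cycle. Later consent is allowed if aspirin is being taken by the end of the cycle 2 day. Section 8.4 allows drug to be mailed, with receipt confirmed by the team.

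**Analysis population.** Section 13.1 offers one set: "The analysis set will include data from the study cohort for the duration of the defined study period". The subsection on missing values, censoring and discontinuations (printed 8.7.3, under 13.4) adds: "An intention-to-treat analysis will be performed for all enrolled subjects".

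**Safety outcome.** The subsection on hypothesis and method (printed 8.7.2, under 13.4) says: "The primary safety outcome is the incidence of clinically significant adverse drug events". Two sentences later it calls for an intention-to-treat analysis, with no restriction to efficacy. Section 6 makes safety a primary objective and refers its analysis to 13.4.

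**A second population.** Section 7.4 states: "Evaluable subjects are participants who are enrolled in the study, given the study drug (aspirin) and receiving NACT until interval debulking surgery". No analysis uses this definition.

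**Adverse events.** Section 11.1 begins: "An adverse event (AE) is any untoward medical occurrence in a subject receiving study therapy". Its recording window is wider: "From the time the subject signs the informed consent form through the End of Study visit".

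**The concern.** Intention-to-treat in all enrolled women is a defensible choice for the VTE rate. The safety rate asks a different question: how often do women who take this drug have an adverse drug event? A woman who took no study tablet generally cannot contribute an event caused by it, yet under the stated rule she counts as event-free. Examples are a woman who changes her mind after consent or whose chemotherapy never starts.

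The trial has a single arm, so there is no control group in which the same dilution would occur. The safety rate will be read in absolute terms, and it answers a primary objective. Because the two populations in the document conflict and neither is assigned to safety by name, an analyst would also have to choose the denominator without a rule, possibly after seeing the data.

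**Working it through.** **1. The plan's own figure.** The only precision figure is a width of 0.098 for the exact 95% interval at a VTE rate of 6.4% (printed 8.7.2). Planned enrolment is 60 + 60 = 120 (Section 7.1). Then 0.064 × 120 = 7.68, rounded to 8 events. The Clopper-Pearson interval for 8/120 is 2.92% to 12.71%, a width of 0.0979, which matches. With 60 women and 4 events the width would be 0.1435. The figure therefore fits a denominator of all 120 planned enrolled women. It concerns efficacy and does not itself test the safety point.

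**2. The dilution formula.** Let f be the share of enrolled women who never took study aspirin, and assume that none of them has a qualifying event. Then

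rate in all enrolled = (1 − f) × rate in treated women.

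**3. Inputs.** N = 120, from the plan. The documents give neither f nor an expected number of adverse drug events. I assume f = 5%, 10% and 15%, and 6 women with an event, for illustration.

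**4. Results (exact 95% intervals).**

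| Denominator | Events / women | Rate | 95% CI |
|---|---|---|---|
| All enrolled | 6/120 | 5.0% | 1.9% to 10.6% |
| Treated, f = 5% | 6/114 | 5.3% | 2.0% to 11.1% |
| Treated, f = 10% | 6/108 | 5.6% | 2.1% to 11.7% |
| Treated, f = 15% | 6/102 | 5.9% | 2.2% to 12.4% |

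With no events, the upper limit is 3.0% for 120 women and 3.4% for 108. At the 0.5% major bleeding rate cited in Section 5.2.2, f = 10% gives 0.5% × 0.9 = 0.45%. If f = 0, all rows are the same.

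**5. Whether the evaluable set would serve instead.** It has three conditions: enrolled, given aspirin, and receiving chemotherapy until interval debulking surgery. The third removes a treated woman who stops chemotherapy early or never has surgery, although she was exposed to the drug. The second is met by being given the drug, which is not the same as taking it. The definition therefore loses exposed women and may keep unexposed ones.

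**The case against.** Several points on the other side are sound.

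- **No sentence names the safety denominator.** A reader might infer that the plan expressly divides adverse drug events by all consented women. It does not; that is the natural reading of printed 8.7.2 and 8.7.3 together. The definition of an adverse event in Section 11.1 points towards women receiving therapy. But that definition settles which events count, not who is in the denominator. If the natural reading were rejected, a primary outcome would have no stated denominator and would need the same repair.
- **Intention-to-treat is not the only population in the document.** Section 7.4 describes another. What stands is that only the intention-to-treat population is tied to an analysis.
- **The bias need not always be favourable.** Women already on low dose aspirin are eligible, so one who never takes a study tablet could still bleed on her own supply. Events are also recorded from consent, before any tablet, and minor bleeding is defined without attribution to the study drug. The dilution is the general direction, not a certainty.
- **The evaluable definition does not remove women because they bled.** A reader might infer this, but a woman who stops aspirin for a bleed and continues chemotherapy to surgery still meets it.
- **The never-treated share may be low.** Participants must be receiving neoadjuvant chemotherapy, staff hand over the drug, and mailed drug is confirmed as received.
- **The effect is small, and no decision hangs on it.** The shift of 0.3 to 0.9 percentage points compares with an interval about 9 points wide, and the plan sets no numerical safety threshold.

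These limit the size and the wording of the concern. They do not supply a suitable safety denominator.

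**Conclusion.** The concern holds in a limited form. Section 13 ties all its analyses to enrolled, meaning consented, women. Nothing exempts the primary safety outcome, and no at-least-one-dose set exists anywhere in the document. Following the rule as written would generally understate the adverse drug event rate by the fraction f. At the assumed 5% to 15%, a reported 5.0% corresponds to 5.3% to 5.9% in treated women, and the upper confidence limit moves from 10.6% to between 11.1% and 12.4%.

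This rests on an assumed f, an illustrative 6 events, full enrolment of 120, and no qualifying events among never-treated women. If every enrolled woman starts aspirin, the effect is zero. The shift is small beside sampling error, but it bears on a primary outcome and is easily avoided, so the text should be changed.

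**What to change.** **In Section 13.1**, define a safety set: all women who took at least one study aspirin tablet, whether or not they completed chemotherapy or reached surgery. The diary alone cannot separate a woman who never started from one whose diary is missing. First-dose status should therefore come from dispensing and receipt records, the diary and visit review together. Count a woman who was dispensed drug but has no diary as treated, unless non-use is documented.

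**In the method subsection (printed 8.7.2)**, compute the incidence of adverse drug events and of bleeding in the safety set, counting events from first dose. Report how many enrolled women were never treated. Keep all enrolled women for the VTE rate.

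**In Section 7.4**, state that the evaluable definition is not used for safety.

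The cost is a few sentences of protocol text, plus a recorded first-dose status drawn mainly from information already collected. The safety rate may be slightly higher and its interval slightly wider. No dose or clinical procedure changes.

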13.5 Interim Analysis

As this is a pilot study, we do not intend to perform any interim analysis. However the study team, including the PI, will review cumulative adverse drug events every 3 months.

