5.2.2. Clinical experience

Aspirin is approved by the FDA use as an antipyretic, anti-inflammatory, and analgesic medication. It is also an approved antiplatelet agent following certain revascularization procedures (cardiac stent placement, e.g.) and to reduce the risk of ischemic stroke or myocardial infarction. Aspirin also has several off-label uses, including for primary prevention of atherosclerotic cardiovascular disease, preeclampsia prevention, and for thromboprophylaxis; the latter provided the foundation for the study concept. Specifically, aspirin was found to be noninferior to other forms of anticoagulation for postoperative thromboprophylaxis following total hip and total knee replacement.[12] Aspirin is also an approved alternative agent for thromboprophylaxis among low risk patients with multiple myeloma receiving thalidomide-based chemotherapy and/or dexamethasone.[13] As an oral agent, aspirin may be a more favorable option for patients with the potential for greater medication adherence. Importantly, unpublished data from our institution demonstrated that aspirin is a more cost-effective option for VTE prophylaxis when compared with apixaban, an alternative oral agent.

Since aspirin is already widely used for a variety of indications, the risks and side effects are well-established. Data regarding bleeding events in the setting of limited duration low dose aspirin use for thromboprophylaxis are reassuring. In a retrospective study of low dose aspirin use for postoperative VTE prevention following total hip arthroplasty, the 90-day bleeding rate was 0.52%. [14] Similarly, a systematic review of low dose aspirin thromboprophylaxis after total hip and knee replacements reported no significant difference in cumulative adverse events between low dose aspirin and other anticoagulants; the event rate for major bleeding among patients receiving aspirin was 0.5% with a significant reduction in the incidence of bruising.[12]

References in Section 15

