Patients receiving chemotherapy are already closely monitored in the outpatient setting with history, physical examination, and lab evaluations prior to every NACT cycle. At each subsequent clinic visit for consideration of an additional NACT cycle, a member of the research team will review medication adherence diaries and AE symptom questionnaires. If symptoms are concerning for a potential AE, the research team personnel will inquire further and discuss with the PI. Please see subsequent sections related to AE monitoring and reporting. No additional components of history and physical exam will be completed outside standard of care performed by the patient's provider prior to initiation of an additional cycle of NACT. Different patients may receive different numbers of cycles, and thus the 30-day supply of aspirin will be re-filled when the decision is made to proceed with an additional cycle.

Any patient with medication intolerance or clinically significant bleeding will be withdrawn from the study to minimize harm. Patients who experience chemotherapy-related thrombocytopenia with platelet count less than 50,000 will be monitored and asked to hold aspirin prophylaxis for 1 week until platelet counts normalize. A designated member of the research team will perform a cumulative review of

adverse events every 3 months and determine if adverse event rates are greater than expected in this patient population.

Performing a pilot study to determine the efficacy and safety of low dose aspirin for thromboprophylaxis when compared with a historical control will help delineate the feasibility of larger studies in the future. This approach mitigates risk while also exploring the potential benefits for patients and the healthcare system overall.

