11.7 Safety Oversight Committee (SOC)

Since this is a pilot phase IV study, the safety oversight committee is not applicable.

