12 QUALITY CONTROL AND QUALITY ASSURANCE

12.1 Monitoring

This clinical research study will be monitored both internally by the PI, and institutionally by the Duke Cancer Institute (DCI). In terms of internal review the PI will continuously monitor and tabulate adverse events. Appropriate reporting to the Duke University Medical Center IRB will be made. If an unexpected frequency of Grade III or IV events occur, depending on their nature, action appropriate to the nature and frequency of these adverse events will be taken. This may require a protocol amendment, dose de-escalation, or potentially closure of the study. The PI of this study will also continuously monitor the conduct, data, and safety of this study to ensure that:

- Interim analyses occur as scheduled;
- Stopping rules for toxicity and/or response are met;
- Risk/benefit ratio is not altered to the detriment of the subjects;
- Appropriate internal monitoring of AEs and outcomes is done;
- Over-accrual does not occur;
- Under-accrual is addressed with appropriate amendments or actions;
- Data are being appropriately collected in a reasonably timely manner.

DCI Protocol Review and Monitoring systems (PRMS) review of this protocol begins with an initial review by the Cancer Protocol Committee (CPC). CPC new protocol review focuses on scientific relevance, study design, adequacy of biostatistical input, protocol prioritization, feasibility of completing the study within a reasonable time frame and risk assessment of the trial. The PI will abide by CPC assessment of the level of risk, which will determine the intensity of subsequent DCI monitoring. CPC also conducts annual scientific progress reviews on protocols that are open to enrollment and focus on protocol prioritization, accrual and scientific progress. These reviews are conducted at the time of IRB annual renewals and documentation of all CPC reviews will be maintained in eIRB/iRIS systems.

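### The 3-monthly review does not name VTE and has no reference rate, and 12.1 relies on scheduled interim analyses and study-level stopping rules that the plan does not contain

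*Combined protocol and SAP*

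**What the plan says.** **Interim analysis and periodic review.** Section 13.5 states: "As this is a pilot study, we do not intend to perform any interim analysis". It then provides that "the study team, including the PI, will review cumulative adverse drug events every 3 months". Safety Considerations (numbered 3.1.2, within Section 7) describes a review at the same interval, by a designated team member, of adverse events more broadly. Its purpose is to "determine if adverse event rates are greater than expected in this patient population". No expected rate or threshold follows in either place.

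**What 12.1 relies on.** Among the things the PI must ensure are "Interim analyses occur as scheduled" and "Stopping rules for toxicity and/or response are met".

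**What exists to satisfy 12.1.** Section 11.6 is titled Stopping Rules, but it deals only with withdrawing one patient or holding her aspirin. Section 11.7 says "the safety oversight committee is not applicable". Section 11.8, headed as the DSMB section, contains only a conflict-of-interest statement. Section 14.6 sends the reader to 11.7 and 11.8 in particular for the monitoring plan.

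**What has already happened.** Sections 3.2 and 5.3 both report an interim analysis of the first 10 recruits, with 3 VTE events.

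**VTE and bleeding.** VTE incidence is the primary endpoint (Section 6), set against a historical rate of about 8%. The adverse events of special interest (numbered 7.1.1, within Section 11) are major bleeding, minor bleeding and intolerance; VTE is not listed. Section 5.2.2 says that "the event rate for major bleeding among patients receiving aspirin was 0.5" percent, in a review of hip and knee replacement.

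**The concern.** In a single-arm prophylaxis trial, too many VTEs is both the efficacy failure and a serious harm. Someone following the written plan would tabulate adverse drug events every 3 months and ask whether they exceed an unstated expectation. The plan would not direct them to count VTEs or to compare the count with the 8% it uses as its control. Section 12.1 reads as if a study-level safeguard existed elsewhere, but none is found in the sections where it should be.

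An early VTE count that was high against the protocol's own benchmark has already been reported. The text gives no rule by which that count was to be judged, and it conflicts with the statement that no interim analysis is intended. Whether a later excess reaches the IRB and the Cancer Protocol Committee (CPC) would depend on individual judgement.

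**Working it through.** **1. Inputs.** Historical VTE rate 8% and target 6.4% (13.4, 13.6). Planned enrolment 60 + 60 = 120 (7.1, Section 10). Early count 3 of 10 (3.2, 5.3). Major bleeding 0.5% (5.2.2).

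**2. The plan's own figure.** Section 13.4 gives a 95% exact interval width of 0.098 at a 6.4% rate. With N = 120, 0.064 × 120 = 7.68, rounded to 8 events. The Clopper-Pearson interval for 8/120 is 2.92% to 12.71%, width 0.0979. The figure reproduces and confirms that 120 is the working size. The plan states no interim or stopping figure to check.

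**3. The early count.** The Clopper-Pearson 95% interval for 3/10 is 6.7% to 65.2%. With X ~ Binomial(10, p):

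P(X ≥ 3) = 1 − P(0) − P(1) − P(2). At p = 0.08 this is 1 − 0.4344 − 0.3777 − 0.1478 = 0.040. At p = 0.064 it is 0.022.

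The two-sided interval still includes 8%; the one-sided 95% lower bound is 8.7%.

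**4. An illustrative VTE trigger.** For each n, take the smallest r with P(X ≥ r | n, 0.08) ≤ 0.05. For the chance of any referral by each look, carry the distribution of events forward over the 10, 20, 30 and 60 women added between looks, and remove paths that have already reached a trigger.

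| n | r | P(X ≥ r) at 8% | P(X ≥ r−1) at 8% | Any referral so far, true 8% | true 12% | true 16% |
|---|---|---|---|---|---|---|
| 10 | 3 | 0.040 | 0.188 | 0.040 | 0.109 | 0.206 |
| 30 | 6 | 0.029 | 0.087 | 0.059 | 0.197 | 0.405 |
| 60 | 9 | 0.048 | 0.104 | 0.088 | 0.352 | 0.681 |
| 120 | 16 | 0.030 | 0.056 | 0.102 | 0.483 | 0.866 |

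Each look is held at 5%, but the four together give about 10% false referrals at 8%. Detection is about 48% at 12% and 87% at 16%.

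**5. Sensitivity to the 8%.** Section 5.3 says most ovarian cancer patients would score an additional Khorana point, so 8% may be too high for women restricted to a score of 1. If the proper reference were 4% (assumed), a doubling to 8% would be referred only about 10% of the time under this table.

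**6. Why bleeding needs a named rate.** P(X ≥ 2 | n = 60) is 0.037 if 0.5% is expected, 0.121 at 1%, 0.338 at 2% and 0.808 at 5% (the last three are assumed rates). The same two bleeds are unusual or routine depending on a figure the plan does not supply.

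**7. The passages side by side.** Section 13.5 schedules no interim analysis, 12.1 requires scheduled ones to occur, and 3.2 and 5.3 report that one took place. Section 12.1 also requires stopping rules for toxicity or response to be met, while 11.6 has rules for individual patients only. These statements cannot all stand as written.

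**The case against.** A reader might infer that an excess of VTE would trigger nothing. The documents do not support that. The adverse event definition in 11.1 is broad enough to include a VTE. A VTE that is life-threatening or leads to admission is serious under 11.2 and goes to the IRB. Section 12.1 has the PI monitor outcomes as well as adverse events, and allows amendment or closure if Grade III or IV events are unexpectedly frequent. It also describes independent monitoring by the cancer institute and annual CPC review. Safety Considerations describes the 3-monthly review as covering adverse events generally, so VTE is unnamed rather than excluded. All of this stands. However, none of these routes names VTE, gives a rate or sets a threshold.

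Two other strong readings also fail. Stopping rules do exist, in 11.6, at patient level; only study-level rules are missing. An interim analysis was reported, so the defect is a contradiction with 13.5.

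The 3/10 should not be read as a 30% rate in the current trial. Khorana score was not an entry criterion before the April 2021 amendment, the scores of those 10 women are not given, and the interval is very wide. Nor does the text say that the count caused the amendment, since guideline endorsement is cited alongside it.

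Finally, numeric triggers in a pilot are partly a matter of preference, and the 0.5% bleeding rate comes from orthopedic surgery. The second objection rules out a fixed bleeding table at 0.5%. The first carries less weight for VTE, because the plan already commits to a periodic review against an expectation and already quotes a VTE rate.

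**Conclusion.** The point holds in this form: the scheduled review neither names the primary outcome nor states a yardstick, no written study-level criterion would require action on an excess of VTE, and 11.6, 12.1, 13.5 and the interim result in 3.2 and 5.3 do not agree. The early count (4.0% tail probability at 8%) shows why a criterion is needed; it does not estimate the VTE rate at Khorana score 1 or show that aspirin fails.

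The operating figures (about 10% false referral at 8%, 48% detection at 12%, 87% at 16%) assume four looks at exactly 10, 30, 60 and 120 women with complete follow-up, independent outcomes and a constant rate. More frequent looks would raise the false-referral rate. This is a change the sponsor should make; it does not affect the primary estimate or its interval.

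**What to change.** 1. In 13.5 and Safety Considerations, name cumulative VTE as an item of the existing 3-monthly review, and give the two descriptions the same scope.
2. State a VTE trigger against the protocol's 8%, for example 3/10, 6/30, 9/60 and 16/120. Reaching it means referral to the IRB and CPC, not an automatic stop.
3. State which women are counted. If the count runs from first enrolment, the first row has already been reached; if it restarts with women enrolled at Khorana score 1, say so.
4. Disclose the operating figures above, and that 8% may be too high for Khorana score 1, in which case an excess is detected late.
5. For bleeding, name and justify a reference rate for women on chemotherapy. Do not take the 0.5% from hip and knee replacement by default.
6. Reconcile 11.6, 11.7, 11.8, 12.1, 13.5 and 14.6 with each other and with 3.2, 5.3 and Safety Considerations, including how the reported interim analysis relates to 13.5.

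The cost is an amendment to wording. VTE and adverse events are already collected, and no visit or test is added. The price of the trigger is an occasional unnecessary referral, about 1 trial in 10 at a true 8%.
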